After Day 8 in-clinic evaluations, patients will return to open-label study drug, through Day 21 (same dose and frequency as at the end of run-in), as prescribed by investigator and dispensed by research pharmacist. No dose adjustments may occur. Patients who were on stable dose of amifampridine phosphate with history of meaningful improvement prior to randomization in CMS-001, will be returned to the same stable dose and frequency during the re-stabilization period.

Period 2 (Days 22-29) (+1 day)

Study medication will be dispensed by the site pharmacist on the last day of the Stabilization Period (i.e. Day 21), according to the randomization schedule. **Patients will start the blinded study medication only after completion of all of the Day 22 assessments, while taking open-label medication, 40 minutes before starting assessments.**

Per the crossover design, patients will receive the double-blind study medication (either amifampridine phosphate tablets or placebo tablets) during Period 2, for 8 days (Day 22 – 29) as an outpatient with a dose of the same medication on the day of scheduled study visit (Day 29), administered by study personnel in the clinic, to facilitate efficacy assessments, under double-blind conditions. If the patient is on a BID or TID regimen during Period 2, the Day 29 assessments should occur after the same dose that corresponds to when assessments were done on Day 0. Any unused portion of dispensed drug will be returned to the site before enrolling the patient in the expanded access program and dispensing open-label drug.

Table 3. Schedule of Events

Study Assessment or Event ^d	Screening ^{qr}	Run-in (up to 4 weeks) ^a		Period I		Re-stabilization		Period II
		Start of Run-in	Last Visit	Days 1-8		Days 9-21		
		Days -14 to -1	Day 1	Day 0 ^{b, c}	Days 1-7	Day 8 ^c (+1 d)	Days 9-20	Day 21 ^c (+1 d)
Informed consent ^e	X							
Inclusion/exclusion criteria	X		X					
Randomization			X					
Medical history	X		X ^f					
CMS genetic testing ^g	X							
Complete physical exam ^h	X							
Abbreviated physical exam ⁱ			X		X		X	
Vital signs	X		X		X		X	
12-Lead ECG	X							
Clinical laboratory tests	X		X		X			
Pregnancy test ^j	X		X				X	
IP dispense		X	X ^k		X ^l		X ^k	X
IP Administration ^{m,p}		X		X ⁿ	X ⁿ	X ⁿ	X ⁿ	X ⁿ

Table 3. Schedule of Events

Study Assessment or Event ^d	Screening ^{qr}	Run-in (up to 4 weeks) ^a		Period I		Re-stabilization		Period II
		Start of Run-in	Last Visit	Days 1-8		Days 9-21		

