The site pharmacy will dispense bottles containing blinded amifampridine phosphate or placebo tablets, depending on the patient's Treatment Sequence assignment, for daily outpatient administration for 7 days (Days 1-7). Administration of blinded study medication will begin with the next scheduled dose following the Day 0 baseline assessment on open-label medication. (see Section 13.3).

13.3 Period 1

Administration will be continued on an outpatient basis for a total of 7 days (Days 1-7).

On Day 8 (+1) patients will be given a dose of the same study medication as the previous 7 days by the study personnel, at the site, so that the assessments/procedures listed below will be completed in relation to the time of study medication dosing.

- Assessment of AEs/SAEs;
- Abbreviated physical exam with weight;
- Vital signs (seated position), including SBP, DBP, heart rate, respiration, and body temperature;
- Clinical laboratory tests;
- Concomitant medications;
- IP accountability;
- Efficacy assessments, including:
 - MFM 20 or 32;
 - SGI (patient/parent/guardian/caregiver);
 - Stimulated Single fiber EMG (optional);
 - CGI-S;
 - CGI-I; and

- Slurp test (optional).

Assessment	Start Time After Dose* (± 10 minutes unless otherwise specified)
SGI	40 minutes
MFM 20 or 32	after SGI
Stimulated Single fiber EMG	after MFM
Slurp test, CGI-S and CGI-I	At end of assessments

*Administration of medication represents Time 0 (minutes)

If the stimulated single fiber EMG (optional assessment) is not to be performed, then the slurp test (also optional), CGI-S and CGI-I assessments should be done following completion of the MFM.

Open-label amifampridine phosphate will be dispensed at the Day 8 visit for administration during the stabilization period, starting with the next scheduled dose after Day 8 assessments (see Section 13.4).

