13.4 Re-stabilization Period

Patients will return to their prior open-label amifampridine phosphate dose established in the run-in phase for 2 weeks, Day 9 through Day 21.

Patients will report to the study site on Day 21 (+1 day) and have the assessments/procedures listed below completed.

- Assessment of AEs/SAEs;
- Abbreviated physical exam with weight;
- Vital signs (seated position), including SBP, DBP, heart rate, respiration, and body temperature;
- Urine pregnancy test in females of childbearing potential only;
- Concomitant medications;
- IP accountability;
- Efficacy assessments, including:
 - MFM 20 or 32;

- SGI (patient/parent/guardian/caregiver);
- CGI-S;
- CGI-I; and
- Slurp test (optional).

Assessment	Start Time After Dose* (\pm 10 minutes unless otherwise specified)
SGI	40 minutes
MFM 20 or 32	after SGI
Slurp test, CGI-S and CGI-I	At end of assessments

*Administration of medication represents Time 0 (minutes)

A The slurp test (optional), CGI-S and CGI-I assessments should be done following completion of the MFM.

The site will dispense bottles containing amifampridine phosphate or placebo tablets, depending on the patient's Treatment Sequence assignment, for Period 2 (Days 22-28). Administration of blinded study medication will begin with the next scheduled dose after Day 21 assessments are completed (see Section 13.5).

13.5 Period 2

Patients will the blinded study medication they did not receive in Period 1. Administration will be continued on an outpatient basis for a total of 7 days (Days 22-28).

Patients will report to the study site on Day 29 (+1 day) and receive a dose of the same study medication they received for the previous 7 days, under the supervision of the study personnel, in order to time the following assessments/procedures in relation to the medication dose.

- Assessment of AEs/SAEs;
- Complete physical exam with weight;
- Vital signs (seated position), including SBP, DBP, heart rate, respiration, and body temperature;
- Standard resting 12-lead ECG;
- Clinical laboratory tests;

- Urine pregnancy test in females of childbearing potential only;
- Concomitant medications;
- IP accountability;
- Efficacy assessments, including:
 - MFM 20 or 32;
 - SGI (patient/parent/guardian/caregiver);
 - Stimulated single fiber EMG (optional);
 - CGI-S;
 - CGI-I; and
 - Slurp test (optional).

Assessment	Start Time After Dose* (± 10 minutes unless otherwise specified)
SGI	40 minutes
MFM 20 or 32	after SGI

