A mixed effects linear model will be fit to each of the MFM datasets described above with percent outcome or individual item scores (as appropriate for each dataset) as the response variable. The model will include fixed effect terms for treatment, period, age group (2 to less than 6 years, 7 to less than 12 years, 12 to less than 17 years of age, and 17 years of age and above), genetic mutation type (see Table 2.2-1), and sequence*period, where sequence corresponds to the order in which the subject received treatments, and a random effect for subject. No carryover term will be fit. In the case of the MFM percent outcome datasets for the adult only patients, the age group fixed effect term will not be included in the model. The LSMeans for the treatment groups will be calculated and provided, as will the estimated difference along with a 95% confidence interval for this difference and a formal hypothesis test that difference in the means is 0. Note that it is highly likely that some specific mutations will have insufficient subjects to fit the specified model. In that case a notation will be made in the relevant table(s) that there are not sufficient observations to fit the model.

Special care must be taken in crossover designs to ensure that there is no significant carryover effect; however, the pharmacological properties of amifampridine (an elimination half-life of 1.8-2.5 hours) are such that having a 12-day restabilization period will minimize any unequal carryover effects in the analysis.

Clinical Global Impression

CGI-S and CGI-I will be summarized by frequency tables and percentages for each sequence group and period. The values will be analyzed with a Wilcoxon rank-sum test as outlined in Putt and Chinchilli (2004). The treatment effects will be estimated using the Hodges-Lehmann estimator and a 90% asymptotic confidence interval.

Single Fiber Electromyogram

Summary statistics for mean jitter, median jitter, and percent block will be presented by treatment and visit. No formal inferential procedures will be performed for these data.

Slurp Test

Summary statistics for the time to slurp sound from the slurp test and its CFB (Day 0 for Period 1 and Day 21 for Period 2) will be presented. No formal inferential procedures will be performed for these data.

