	Least Squares (LS) Mean of Change from Baseline	xxx	xxx
	Between-Treatment Difference in LS Means (A-B)	xxx	
	Denominator degrees of freedom	x	
	95% CI for Between-Treatment Difference in LS Means (A-B)	(xxx, xxx)	

^a MFM score expressed as a percentage of the maximum possible was modeled as the response, with fixed effects terms for treatment, period, sequence*period (i.e., carryover) and mutation type at Baseline. Individuals measured with the MFM-20 (i.e., aged 2- <7 years) are excluded from the analyses for items in the MFM-32 excluded from the MFM-20.

STATKING Clinical Services (yyyy-mm-dd)

Source Program: xxxxxxx.sas

Table format repeats for PP population. Parts will be included for all subjects, pre- and post- synaptic mutations and each mutation type. Individual items will be ordered in increasing order of the p-values for the Crossover test.

Page x of y

Table 33. Clinical Global Impression Summary by Mutation Type
 Catalyst Pharmaceuticals, Inc. - CMS-001
 FAS Population (N=xxx)

Part x of y: xxxxxxxxxxxx Mutation

Variable	Treatment Sequence	Time Point	Type ^a	1	2	3	4	5	6	7
CGI-Severity	Amifampridine/Placebo	Day 0 (Baseline)	RAW	xxx						
		Day 8	RAW	xxx						
			CFB	xxx						
		Day 21	RAW	xxx						
			CFB	xxx						
		Day 29	RAW	xxx						
			CFB	xxx						
		Day 0 (Baseline)	RAW	xxx						
		Day 8	RAW	xxx						
			CFB	xxx						
		Day 21	RAW	xxx						
			CFB	xxx						
		Day 29	RAW	xxx						
			CFB	xxx						
CGI-Improvement	Amifampridine/Placebo	Day 0 (Baseline)	RAW	xxx						
		Day 8	RAW	xxx						
			CFB	xxx						
		Day 21	RAW	xxx						
			CFB	xxx						
		Day 29	RAW	xxx						
			CFB	xxx						
		Day 0 (Baseline)	RAW	xxx						
		Day 8	RAW	xxx						
			CFB	xxx						
		Day 21	RAW	xxx						
			CFB	xxx						
		Day 29	RAW	xxx						
			CFB	xxx						

^a RAW = observed data entered in the database; CFB = change from baseline = Value at timepoint - Baseline value.

STATKING Clinical Services (yyyy-mm-dd)

Source Program: xxxxxxxx.sas

Table format repeats for PP population. Parts will be included for all subjects, pre- and post- synaptic mutations and each mutation type.

Table 35. Clinical Global Impression Score Mann-Whitney Main Effects Analysis
 Catalyst Pharmaceuticals, Inc. - CMS-001
 FAS Population (N=xxxx)

Subgroup	Variable	Time Point	Hodges-Lehmann Estimate	90% Confidence Limits	Mann-Whitney Test P-value
All Subjects	CGI-Severity	Day 8	xxxx	(xxxx, xxxx)	xxxxxx
		Day 21	xxxx	(xxxx, xxxx)	xxxxxx

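### The CGI inference shell (SAP Table 35, repeated as Table 36) has a Day 21 row, when both sequences are on open-label drug, and no Day 29 or Crossover row, in conflict with SAP 4.2.2

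*SAP*

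**What the plan says.** - **The shell.** SAP Appendix B, Table 35, "Clinical Global Impression Score Mann-Whitney Main Effects Analysis", has columns for a Hodges-Lehmann estimate, 90% confidence limits and a Mann-Whitney p-value. For CGI-S and CGI-I, in all subjects and in every subgroup block, the time points are Day 8 and Day 21. The table list in SAP 7.0 gives Table 36 as the per-protocol repeat.
- **The text.** SAP 4.2.2 says "CGI-S and CGI-I will be summarized by frequency tables and percentages for each sequence group and period". It then plans a Wilcoxon rank-sum test taken from a cited paper on nonparametric analysis of crossover studies, with Hodges-Lehmann treatment effects and a 90% interval.
- **Treatment at each visit.** Protocol 13.3: "On Day 8 (+1) patients will be given a dose of the same study medication as the previous 7 days". Protocol 10.1: "After Day 8 in-clinic evaluations, patients will return to open-label study drug, through Day 21". Protocol 13.4: "Administration of blinded study medication will begin with the next scheduled dose after Day 21 assessments are completed". Protocol 13.5: "Patients will report to the study site on Day 29 (+1 day) and receive a dose of the same study medication they received" over the preceding week. CGI-S and CGI-I are collected at Days 0, 8, 21 and 29.
- **The descriptive shell.** Table 33, "Clinical Global Impression Summary by Mutation Type", shows Days 0, 8, 21 and 29. Only Day 0 is labelled as baseline. Change-from-baseline rows appear for both CGI-S and CGI-I, under score columns 1 to 7.
- **Status of the shells.** SAP Appendix A makes the mock tables the format of the tables to be delivered and says that format changes after SAP approval incur further charges.

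**The concern.** A table of treatment main effects in a two-period crossover should use the two blinded end-of-period visits. This one pairs one of them (Day 8) with the visit that the SAP elsewhere treats as the Period 2 baseline for SGI, MFM and the slurp test (Day 21).

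Two things follow if a programmer works from the shell. The Day 21 row puts an estimate, an interval and a p-value under a main-effects title although both groups are on the same drug. A reader could take a null result there as evidence of no effect, or a chance result as evidence of one. And the blinded Period 2 ratings contribute to no CGI test, so the within-patient comparison, which is the reason for a crossover design, is lost for this measure.

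Table 33 has a related weakness. With Day 0 as the only labelled baseline and a change row at Day 21, the Day 29 change appears to be taken from Day 0 and not from Day 21.

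**Working it through.** **Visits side by side**

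| Visit | AP sequence | PA sequence | Treatment contrast? | In Table 35? |
|---|---|---|---|---|
| Day 8 | blinded amifampridine | blinded placebo | yes, Period 1 | yes |
| Day 21 | open-label amifampridine | open-label amifampridine | none concurrent | yes |
| Day 29 | blinded placebo | blinded amifampridine | yes, Period 2 | no |
| Day 8 and Day 29 combined | amifampridine minus placebo | placebo minus amifampridine | yes, within patient | no |

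Tables 7, 13 and 21 (SGI, MFM-32, MFM-20) each have a Period 1 row and a Crossover row, so the other inference shells report the contrast that is missing here. The finding rests on this comparison and needs no arithmetic.

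**The plan's own power figure.** SAP 1.3 states 90% power for SGI with effect size 0.5 (difference divided by the SD of the difference), 23 patients per sequence and two-sided 0.05. With N = 46 and 44 degrees of freedom, the noncentrality is 0.5 × √46 = 3.39 and the power is 91.3%. The stated figure reproduces.

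**Illustration for CGI.** The documents give no effect size, SD or correlation for CGI. Assumptions: the SGI effect size of 0.5 carries over; 23 patients in total (SAP 1.1), split 12 and 11; the SD of the within-patient difference is set to 1; the correlation ρ between the two period values runs from 0 to 0.7; there is no period effect.

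- Standard-error factor: √(1/12 + 1/11) = 0.417.
- Crossover contrast by t-test: the sequences differ by 2 × 0.5 = 1 on the Period 1 minus Period 2 scale. Noncentrality 1 / 0.417 = 2.40, 21 degrees of freedom, power about 63%.
- Day 8 alone by t-test: the per-period SD is 1 / √(2(1 − ρ)), and the noncentrality is 0.5 / (SD × 0.417).

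| ρ | SD | Noncentrality | Power, Day 8 alone |
|---|---|---|---|
| 0 | 0.71 | 1.69 | 37% |
| 0.5 | 1.00 | 1.20 | 21% |
| 0.7 | 1.29 | 0.93 | 14% |

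The planned test is rank-based. A Mann-Whitney simulation under the same assumptions (normal scores, 4,000 runs per setting) gave about 58% for the crossover contrast, 13% to 33% for Day 8, and 4% to 5% for Day 21, which is type I error only. With 23 patients per sequence the same three were about 89%, 23% to 61%, and about 5%.

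**Scale of the crossover estimate.** Write τ for the amifampridine minus placebo effect and π for the period difference. Period 1 minus Period 2 has location π + τ in AP and π − τ in PA. The shift between sequences is therefore 2τ, so the Hodges-Lehmann shift and both its limits must be halved. Lower CGI scores are better, so benefit appears as a negative τ.

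**The case against.** The strongest reply is that this is a slip in a mock table. SAP 4.2.2 does plan a crossover rank-sum analysis with treatment-effect estimates, and Appendix A fixes the format of the tables without saying that they override Section 4. The shells contain other plain slips: Table 17 is an MFM-32 percent table in the SAP 7.0 list but an MFM-20 score table in Appendix B, and Listing 15 shows a Day 10 ECG. Day 21 may simply be a typing error for Day 29. In addition, the protocol (15.6) plans only summary statistics for CGI, and the SAP ranks it as secondary.

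Most of that stands, and it limits the point. Some stronger readings do not hold:

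- A reader might infer that every row of Table 35 is an open-label comparison. Day 8 is double-blind, and its row is sound.
- A reader might infer that the SAP plans no crossover effect for CGI. The text plans one; the shell has nowhere to report it.
- A reader might infer that the Day 29 ratings go unreported. Table 33 summarises them.
- A reader might treat the power figures as CGI power. They borrow the SGI effect size, and neither the t-test nor the simulation allows for ties on a seven-point scale.

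What does not stand is the view that nothing needs changing. If Day 21 is merely a typing error, correcting it still leaves two separate period comparisons and no Crossover row. The row might also be defended as a check on carryover or baseline balance, but the SAP states no such purpose and the table is titled as a main-effects analysis.

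**Conclusion.** The Table 35 shell, and with it Table 36, conflicts with SAP 4.2.2. As drawn it reports a valid Period 1 comparison, adds a Day 21 test with no concurrent treatment contrast, and omits both Day 29 and the crossover contrast that the text calls for. This follows from the visit schedule and the shells alone.

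The loss of power is illustrative: about 63% for the crossover contrast against 14% to 37% for Day 8 alone by t-test, and slightly lower by rank-sum. It depends on the assumed transfer of the SGI effect size, on 23 patients in total and on the range of correlation shown.

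The consequence is confined to a secondary measure. The SGI shell (Table 7) already has its Crossover row, so the primary conclusion is not affected. The correction should be made before unblinding, so that the CGI contrast is not chosen after the results are known.

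**What to change.** **Tables 35 and 36**
- Keep Day 8, labelled Period 1.
- Replace Day 21 with Day 29, labelled Period 2.
- Add a Crossover row: a rank-sum test between sequences on each patient's Period 1 minus Period 2 value, with the Hodges-Lehmann shift and its limits halved to give the amifampridine minus placebo effect.
- For CGI-S, analyse change from the period baseline (Day 0 for Period 1, Day 21 for Period 2), as for SGI and MFM. For CGI-I, use the raw rating, and state which visit the Day 29 rating is compared with, since Protocol Appendix 4 refers to baseline without giving a date.

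**Tables 33 and 34**
- Label Day 21 as the Period 2 baseline for CGI-S.
- Drop the change-from-baseline rows for CGI-I, which is already a rating of change.
- Tabulate CGI-S change on a scale that allows zero and negative values; it can run from −6 to +6, which columns 1 to 7 cannot hold.

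Add a sentence to SAP 4.2.2 naming the analysed value and the halving. The cost is a correction to the SAP text and shells, plus any reformatting charge under Appendix A. No new data are needed.

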Patients already receiving 3,4-DAP or amifampridine phosphate treatment for CMS, and meeting the applicable inclusion and exclusion criteria are eligible to participate in this study. The patient should report or investigator judges there is a history of meaningful improvement in motor function on 3,4-DAP or amifampridine phosphate treatment; improvement of at least 20% in MFM 20 or 32 is not a requirement for these participants. Patients who are on a stable dose of amifampridine phosphate with a history of meaningful improvement in motor function, they can be randomized into Period 1. The patient should be on that stable dose and frequency of amifampridine phosphate for at least 1 week before being randomized to a Treatment Sequence. Those patients who are on a stable dose of 3,4-DAP will be transitioned to equivalent dose of amifampridine phosphate for 7 days prior to randomization to treatment.

Procedures/assessments, as detailed in [Table 3](#), will be conducted before starting Period 1 study medication (i.e. Day 0). Administration of Period 1 study medication (amifampridine phosphate or placebo) begins after all assessments have been completed on Day 0. Every attempt should be made to have the same individual perform all assessments for a patient throughout the study, and after the same dose used for Day 0 assessments. Following Period 1, patients will be returned to the same stable dose administered at the end of the open-label run-in period for days 9-21, followed by Period 2 dosing for 8 days. Patients who were on a stable dose of amifampridine phosphate with history of meaningful improvement prior to randomization in CMS-001, will be returned to the same stable dose from days 9-21, followed by Period 2 dosing for 8 days. After completion of the study, patients will be eligible for expanded access program and receive open-label amifampridine phosphate at the same dose and frequency as established in the run-in phase of the study. Patients who were on stable dose of amifampridine phosphate with a history of meaningful improvement prior to randomization in CMS-001, will be returned to the same stable dose and frequency during

their participation in the expanded access program.

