13 STUDY PROCEDURES

13.1 Screening Visit

An ICF must be signed and dated by the patient, parent or legal guardian, the investigator or designee, and witness (if required) before any study-related procedures are performed. Refer to Section 10.4 for prohibited medications.

After ICF signed, the patient will be screened for enrollment into the study. The study activities listed below will be performed during the 1 to 14 days that constitute the Screening visit.

- Informed Consent;
- Assessment of Inclusion/Exclusion criteria;
- Demographics (sex, race, ethnic origin, age);
- Medical history, including allergy history and number of hospitalizations or ER visits in last 6 months;
- CMS genetic testing, if not previously done and report available;
- Standard resting 12-lead ECG;
- Complete physical examination including weight and height;
- Vital signs (seated position), including systolic blood pressure (SBP), diastolic blood pressure (DBP), heart rate, respiration, and body temperature;
- Clinical laboratory tests;
- For females of child bearing potential, a serum pregnancy test will be taken at Screening.;
- MFM 20 or 32;
- Stimulated single fiber EMG (optional);
- CGI-S;
- Slurp test (optional);
- Assessment of SAEs; and
- Assessment of concomitant medications.

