xxxxxxxxxx	CGI-Improvement	Day 8	xxxx	(xxxx, xxxx)	xxxxxx
		Day 21	xxxx	(xxxx, xxxx)	xxxxxx
xxxxxxxxxx	CGI-Severity	Day 8	xxxx	(xxxx, xxxx)	xxxxxx
		Day 21	xxxx	(xxxx, xxxx)	xxxxxx
xxxxxxxxxx	CGI-Improvement	Day 8	xxxx	(xxxx, xxxx)	xxxxxx
		Day 21	xxxx	(xxxx, xxxx)	xxxxxx
xxxxxxxxxx	CGI-Severity	Day 8	xxxx	(xxxx, xxxx)	xxxxxx
		Day 21	xxxx	(xxxx, xxxx)	xxxxxx
xxxxxxxxxx	CGI-Improvement	Day 8	xxxx	(xxxx, xxxx)	xxxxxx
		Day 21	xxxx	(xxxx, xxxx)	xxxxxx

STATKING Clinical Services (yyyy-mm-dd)
 Source Program: xxxxxxxx.sas

Table format repeats for PP population.
 Subgroups will be included for all subjects, pre- and post-synaptic mutations and each mutation type.

Table 37. Summary Statistics for Single Fiber Electromyogram Measurements
 Catalyst Pharmaceuticals, Inc. - CMS-001
 FAS Population (N=xxx)

Treatment Sequence	Variable	Time Point	Data Type ^a	Mean	Std Dev	n	Min	Max	Median
Amifampridine/Placebo	xxxxxxxx	Screening (Baseline)	RAW	xxx	xxx	xxx	xxx	xxx	xxx
		Day 8	RAW	xxx	xxx	xxx	xxx	xxx	xxx
			CFB	xxx	xxx	xxx	xxx	xxx	xxx
		Day 29	RAW	xxx	xxx	xxx	xxx	xxx	xxx
	xxxxxxxx		CFB	xxx	xxx	xxx	xxx	xxx	xxx
		Screening (Baseline)	RAW	xxx	xxx	xxx	xxx	xxx	xxx
		Day 8	RAW	xxx	xxx	xxx	xxx	xxx	xxx
			CFB	xxx	xxx	xxx	xxx	xxx	xxx
Placebo/Amifampridine	xxxxxxxx	Day 29	RAW	xxx	xxx	xxx	xxx	xxx	xxx
			CFB	xxx	xxx	xxx	xxx	xxx	xxx

^a RAW = observed data entered in the database; CFB = change from baseline = Value at timepoint - Baseline value.
 STAKING Clinical Services (yyyy-mm-dd)
 Source Program: xxxxxxxx.sas

Table format repeats for PP population.
Variable will correspond to one of the following: Mean Jitter, Median Jitter, and Percent Block

Table 39. Summary Statistics for Slurp Test Measurement by Treatment, Period and Time Point
 Catalyst Pharmaceuticals, Inc. - CMS-001
 FAS Population (N=xxx)

Treatment	Time Point	Data Type ^a	Std					Median
			Mean	Dev	n	Min	Max	
Amifampridine/Placebo	Day 0 (Baseline)	RAW	xxx	xxx	xxx	xxx	xxx	xxx
	Day 8	RAW	xxx	xxx	xxx	xxx	xxx	xxx
	Day 8	CFB	xxx	xxx	xxx	xxx	xxx	xxx
	Day 21 (Baseline)	RAW	xxx	xxx	xxx	xxx	xxx	xxx
	Day 29	RAW	xxx	xxx	xxx	xxx	xxx	xxx
	Day 29	CFB	xxx	xxx	xxx	xxx	xxx	xxx
	Day 0 (Baseline)	RAW	xxx	xxx	xxx	xxx	xxx	xxx
	Day 8	RAW	xxx	xxx	xxx	xxx	xxx	xxx
	Day 8	CFB	xxx	xxx	xxx	xxx	xxx	xxx
Placebo/Amifampridine	Day 21 (Baseline)	RAW	xxx	xxx	xxx	xxx	xxx	xxx
	Day 29	RAW	xxx	xxx	xxx	xxx	xxx	xxx
	Day 29	CFB	xxx	xxx	xxx	xxx	xxx	xxx

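### SAP Table 37 takes single-fiber EMG change from a Screening recording that is off drug in naive patients and on drug in pre-treated ones, so the size of the change depends on the prior-exposure mix

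*SAP*

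**What the plan says.** The shell in SAP Appendix B titled "Table 37. Summary Statistics for Single Fiber Electromyogram Measurements" labels its first row for each sequence "Screening (Baseline)". It then gives raw values and change from baseline at Day 8 and Day 29, with the footnote "CFB = change from baseline = Value at timepoint - Baseline value". Both periods therefore subtract the same Screening value. The rows are by treatment sequence and are not split by prior exposure.

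SAP 4.2.2 says less: "Summary statistics for mean jitter, median jitter, and percent block will be presented by treatment and visit", followed by "No formal inferential procedures will be performed for these data". It defines no SFEMG baseline or change. For the slurp test, the same section uses period baselines: "its CFB (Day 0 for Period 1 and Day 21 for Period 2) will be presented". Protocol 15.6 asks for SFEMG summaries by treatment and period; among the descriptive endpoints it attaches change from baseline only to CGI-S.

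Protocol 13.1 lists "Stimulated single fiber EMG (optional)" at Screening. Sections 13.3, 13.5 and 13.6 list the test at Day 8, Day 29 and early discontinuation. It is absent from the Day 0 list (13.2) and the Day 21 list (13.4).

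On who is screened, Protocol 10.1 states: "Patients already receiving 3,4-DAP or amifampridine phosphate treatment for CMS, and meeting the applicable inclusion and exclusion criteria are eligible to participate in this study". No washout before Screening is described, and exclusion criterion 7 exempts these drugs. Naive patients first receive drug on Day 1 of the run-in.

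**The concern.** A change from baseline is readable only if baseline means the same thing in every patient. Here it has two meanings. In a naive patient, Screening is the untreated state, so change on drug shows the drug effect and change on placebo is about zero. In a pre-treated patient, Screening already contains some or all of the effect, so change on drug shrinks towards zero and change on placebo shows the loss of effect. Table 37 averages the two kinds of patient in unreported proportions.

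The timing of Screening adds to this. Table 3 footnote d requires standardized times relative to dosing, and Section 10.3.3 ties those times to a dose given in the clinic, with SGI starting at 40 minutes. Section 13.1 lists no dose, no SGI and no timing table, whereas Sections 13.2 to 13.5 each have one. The rule has nothing to anchor it at Screening.

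At stake is the reading of a secondary efficacy variable (SAP 4.1.2) that is the only electrophysiological measure in the trial. Protocol 8.6 cites the lack of such measures in earlier studies as part of the rationale.

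**Working it through.** The documents give no SFEMG effect, SD or sample size, so there is no stated figure to reproduce. The check is algebra on the Table 37 definition.

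**Inputs**
- d: amount by which the drug lowers jitter or block at the Day 8 and Day 29 post-dose time. Not given; results are in units of d.
- p: share of pre-treated patients among those recorded. Not given; range 0 to 1.
- f: fraction of d present at Screening in pre-treated patients. Not given; range 0 to 1.
- Assumed: the same d in both kinds of patient, placebo equal to the untreated state by the end of a period, no period effect, and naive patients recorded before their first dose. Table 3 footnote q allows Screening and Day 1 to be one visit and does not state the order.

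**Change from Screening.** Relative to untreated, the mean Screening value is -pfd.
- On amifampridine: -d - (-pfd) = -(1-pf)d
- On placebo: 0 - (-pfd) = +pfd
- Amifampridine minus placebo in the same patients: -(1-pf)d - pfd = -d

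| p | drug, f = 1 | placebo, f = 1 | drug, f = 0.5 | placebo, f = 0.5 | paired difference |
|---|---|---|---|---|---|
| 0 | -d | 0 | -d | 0 | -d |
| 0.25 | -0.75d | +0.25d | -0.875d | +0.125d | -d |
| 0.5 | -0.50d | +0.50d | -0.75d | +0.25d | -d |
| 0.75 | -0.25d | +0.75d | -0.625d | +0.375d | -d |
| 1 | 0 | +d | -0.50d | +0.50d | -d |

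With f = 0 the drug column is -d and the placebo column 0 for every p.

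**Why f is poorly determined.** Protocol 8.5 gives a half-life of 1.8 hours. Under first-order elimination, the plasma level falls to 0.5^(h/1.8) of its starting value after h hours: 68% at 1 h, 46% at 2 h, 21% at 4 h and 10% at 6 h. These are concentrations, not effects on jitter, but they show that time since dose matters.

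**Comparing sequences at Day 8.** Let p1 be the pre-treated share in the sequence on amifampridine first and p2 the share in the other. The difference in change from Screening is

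-(1-p1·f)d - p2·f·d = -d + (p1-p2)fd.

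With f = 1 and shares of 75% and 25%, it is -d + 0.5d = -0.5d. With the shares reversed it is -1.5d. The true value is -d. An assumed 3 of 4 against 1 of 4 pre-treated gives the same 0.5d shift. At Day 29 the treatments swap, so the amifampridine-minus-placebo difference is -d + (p2-p1)fd: an equal shift the other way.

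**The case against.** The strongest reply is that little depends on this change score. SFEMG is optional, is not done at every site and carries no inference. The change exists only in a table shell. Raw values are printed beside it, and sequence plus visit identifies the treatment, so a reader can recover the difference in means; the common Screening value cancels when the two visits are subtracted. Data Listing 14 also gives each patient's values. All of this stands and limits the importance. What remains is that the SD of the paired difference cannot be obtained from Table 37, because it needs the correlation between visits, and no summary pooled over periods is printed. The change will be produced unless the shell is altered, since Appendix A makes the shell the deliverable format.

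Three stronger readings are tempting, and the documents do not support them.
- A reader might infer that the sign of the change depends on the mix. For f from 0 to 1, no cell reverses: the drug cell stays at or below zero and the placebo cell at or above it. Reversal needs a Screening effect larger than that at Day 8 or Day 29 (f = 1.2 with p = 1 gives +0.2d on drug), or an average over both visits, which Table 37 does not print.
- A reader might call the Day 8 comparison biased. Sequences are randomized 1:1, so p1-p2 has expectation zero and a chance imbalance is imprecision. No stratification by prior exposure is described, but the plan also makes no formal between-sequence SFEMG comparison.
- A reader might call the Screening time uncontrolled. Footnote d does set a rule; the gap is that the rule lacks a dose to refer to at that visit.

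**Conclusion.** The point holds as one about size and interpretation. Change from Screening in Table 37 mixes off-drug and on-drug baselines. The printed change on amifampridine is -(1-pf)d, anywhere from -d to 0, and on placebo +pfd, anywhere from 0 to +d, for the same true effect. Chance imbalance in prior exposure can move a Day 8 between-sequence comparison by up to (p1-p2)d. That limit assumes a Screening effect no larger than the on-treatment effect; p, f and d are assumptions shown over a range. The within-patient contrast is -d whatever p and f are. Neither Protocol 15.6 nor SAP 4.2.2 asks for this change score. The primary conclusion and every inferential result are unaffected, so this is a low-priority correction.

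**What to change.** In Table 37, replace change from Screening with the within-patient amifampridine-minus-placebo difference, taken from Day 8 and Day 29 with its sign set by sequence. Give its mean, SD and n for mean jitter, median jitter and percent block. Present raw values by treatment and period, as Protocol 15.6 asks. Show Screening values as description only, split into naive and already-treated patients, and state the same in SAP 4.2.2.

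The cost is a wording change in the SAP and shell and a small programming change, including a prior-exposure flag, for which prior medications are already collected (Protocol 10.4). No extra recording is needed. The downside is that a patient with only one of the two on-treatment recordings leaves the paired row, though that recording stays in the raw summaries.
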